#### **5.3.2.4. Exposure**

No imputation will be done for first dose date. Date of last dose of study drug, if unknown or partially unknown, will be imputed as follows:

- If the last date of study drug is completely missing and there is no End of Treatment eCRF page and no death date, the patient should be considered to be ongoing and use the cut-off date for the analysis as the last dosing date
- If the last date of study drug is completely or partially missing and there is EITHER an End of Treatment eCRF page OR a death date available (within the cut-off date), then imputed last dose date is:
  - = 31DECYYYY, if only Year is available and Year < Year of min (EOT date, death date)
  - = Last day of the month, if both Year and Month are available and Year = Year of min (EOT date, death date) and Month < the month of min (EOT date, death date)
  - = min (EOT date, death date), for all other cases.

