#### **5.2.7. Definition of on-treatment period**

Safety endpoints will be summarized based on the on-treatment period unless otherwise specified.

On-treatment period is defined as the time from the first dose of study treatment through minimum (30 days + last dose of study treatment, start day of new anti-cancer drug therapy – 1 day).

Safety data collected outside the on-treatment period as described above will be listed and flagged in listings but not summarized.

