YYYY = Year of min [max(PD date + 1, last dose of study treatment + 1), end date of new anti-cancer therapy], AND

MMM = Month of min [max(PD date + 1 day, last dose of study treatment + 1 day), end date of new anti-cancer therapy]

THEN

imputed start date = min [max(PD date + 1 day, last dose of study treatment + 1 day), end date of new anti-cancer therapy];

ELSE IF

YYYY = Year of min [max(PD date + 1, last dose of study treatment + 1), end date of new anti-cancer therapy], AND

MMM > Month of min [max(PD date + 1 day, last dose of study treatment + 1 day), end date of new anti-cancer therapy]

THEN

imputed start date = 01 MMM YYYY;

ELSE IF

YYYY < Year of min [max(PD date + 1, last dose of study treatment + 1), end date of new anti-cancer therapy]

THEN

imputed start date = DAY (Last day of MMM) MMM YYYY;

ELSE IF

YYYY > Year of min [max(PD date + 1, last dose of study treatment + 1), end date of new anti-cancer therapy]

THEN

imputed start date = 01 MMM YYYY.

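### The last-dose imputation rule overrides a recorded month and year whenever the end-of-treatment or death date falls in a later calendar year

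*SAP*

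**What the plan says.** SAP 5.3.2.4 covers an incomplete last-dose date for a patient who has an EOT page or is known to have died. Its condition opens: "If the last date of study drug is completely or partially missing and there is EITHER an End of Treatment eCRF page OR a death". Call the earlier of the EOT date and the death date the reference date. There are three outcomes:

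1. 31 December of the recorded year, "if only Year is available and Year < Year of min (EOT date, death date").
2. The last day of the recorded month, "if both Year and Month are available and Year = Year of min (EOT date, death date") and also "Month < the month of min (EOT date, death date").
3. The reference date itself: "min (EOT date, death date), for all other cases".

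SAP 5.3.3.4, on the start of new anti-cancer therapy, is built in a similar way but has one more branch. Where month and year are known and "YYYY < Year of min [max(PD date + 1, last dose of study treatment + 1), end date of new anti-cancer therapy"], it sets "imputed start date = DAY (Last day of MMM) MMM YYYY", so the recorded month is kept.

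The last-dose date is used in several places. SAP 5.2.7 states: "On-treatment period is defined as the time from the first dose of study treatment through minimum (30 days + last dose of study treatment", or the day before new anti-cancer drug therapy if that is sooner). The date also enters duration of exposure for each drug (6.5.3.1, 6.5.3.2), the axitinib RDI denominator (6.5.3.2), the count of deaths within 30 days of last dose (6.6.2) and the 90-day window for immune-related events (Appendix 1).

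**The concern.** Outcome 2 requires the two years to be equal. A record such as --/NOV/2016 with an EOT date in January 2017 fails outcome 1, because the month is known, and fails outcome 2, because the years differ. It therefore takes the January date, which contradicts both the month and the year that the site recorded.

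The results are also incoherent. A record of 2016 alone is placed on 31 December 2016. A record of November 2016, which carries more information, is placed later, in January 2017. Within one calendar year the rule respects the recorded month, and the SAP gives no reason for dropping that principle at 1 January.

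At stake is the accuracy of exposure duration and, under conditions, of axitinib RDI and of which events and deaths fall inside the safety windows.

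**Working it through.** No stated figure in the plan depends on this rule, so there is none to reproduce. The check applies the three outcomes literally and compares the result with the last day of the recorded month. Calendar years and days are illustrative.

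| Recorded last dose | Reference date | Outcome reached | Date under SAP 5.3.2.4 | End of recorded month | Excess |
|---|---|---|---|---|---|
| --/OCT/2016 | 10 Dec 2016 | 2 | 31 Oct 2016 | 31 Oct 2016 | 0 days |
| 2016 only | 10 Jan 2017 | 1 | 31 Dec 2016 | not applicable | not applicable |
| --/DEC/2016 | 10 Jan 2017 | 3 | 10 Jan 2017 | 31 Dec 2016 | 10 days |
| --/NOV/2016 | 10 Jan 2017 | 3 | 10 Jan 2017 | 30 Nov 2016 | 31 + 10 = 41 days |

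The first two rows behave as intended and the last two do not. For a November record, reference dates from 1 to 31 January give an excess of 31 + 1 = 32 to 31 + 31 = 62 days. For a December record the range is 1 to 31 days. All 144 pairings of a recorded month in one year with a reference month in the next give a date outside the recorded month.

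**Duration of exposure.** Assume a first axitinib dose on 1 June 2016. Duration in weeks is (last date − first date + 1)/7.
- To 30 November: 183/7 = 26.1 weeks.
- To 10 January: (183 + 41)/7 = 224/7 = 32.0 weeks.

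**Axitinib RDI.** SAP 6.5.3.2 divides cumulative dose by 14 × d × duration, where d is the planned dose per intake.
- If dosing was full to 30 November and cumulative dose stays fixed, RDI is 183/224 = 81.7% instead of 100%.
- The same calculation for a December record gives (183 + 31)/224 = 214/224 = 95.5%.
- If cumulative dose is accumulated up to the imputed stop date, numerator and denominator grow together and RDI hardly moves.

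The SAP defines cumulative dose only as the total actually received and does not say which treatment applies.

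**Safety windows.** In the November example, last dose plus 30 days moves from 30 December to 9 February. SAP 3.4.1 takes the last dose of study treatment as the later of the two drugs' last non-zero doses. A known dose of the other drug on or after 10 January therefore leaves all three windows unchanged, and one between 30 November and 10 January reduces the shift. The on-treatment window also stops the day before new anti-cancer drug therapy. The 90-day immune-related window ignores that cut-off.

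**The case against.** The literal reading is not in dispute: no other text in the SAP closes this case. Reading outcome 1 loosely to cover it would give 31 December, which suits a December record but contradicts any other month. The serious objections concern weight.

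- **Likelihood.** Avelumab is infused at the site and the exact infusion duration is recorded (Protocol 5.3.3.1), so a month-only date is implausible. For axitinib there is a patient diary, and remaining tablets are counted at each clinic visit (Protocol 5.2). The study projects about 55 patients (SAP 2.2), and imputed values are flagged in listings (SAP 5.3.1). This stands: the case should be rare. Flagging, however, does not correct the summary tables.
- **The 41-day example.** Follow-up visits run every 30 days (±3) from last dose (Protocol Schedule of Activities). After a 30 November last dose the Day 30 visit is due by about 2 January, so an EOT date of 10 January would come after it. A treatment hold, or continuing the other drug, could produce the gap, but it is not the plain case. SAP 5.3.2.4 also does not say whether the EOT date is a visit date or a discontinuation date. This stands, so the 10-day December case belongs beside it.
- **The comparator.** SAP 5.3.3.4 governs a different variable. It supports the fix by analogy and is not itself a contradiction.
- **A longer window is cautious for safety.** The SAP does not claim this, and outcome 2 does not follow it within a year.

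A reader might infer that the rule always lowers RDI and always turns later events into treatment-emergent ones. The documents do not support that. The RDI effect depends on an unstated handling of cumulative dose, and the event effect depends on the other drug's last dose and the new-therapy cut-off. Overall avelumab RDI is unaffected, because its denominator runs to the end of the last cycle with a non-zero dose, counted from that cycle's start (SAP 6.5.3.1).

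**Conclusion.** The rule as written gives a wrong date for a known month in an earlier year than the reference date. The case is not undefined: the catch-all assigns a date, and that date contradicts the record. Against the end of the recorded month, the excess with EOT on 10 January is 10 days for a December record and 41 days for a November record, assuming no death date before the EOT date.

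When the case occurs, that drug's duration of exposure is lengthened. The effects on axitinib RDI and on the three safety windows hold only under the conditions shown above. The documents do not give the number of patients affected, and it is probably very small.

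It would be wrong to infer any threat to the primary result. DLTs are counted over the first 4 weeks of combination treatment in the DLT-evaluable set, and no dose-finding decision uses this imputed date. This is a minor drafting correction.

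**What to change.** Rewrite the second outcome in SAP 5.3.2.4 so that the last day of the recorded month is used when month and year are both known and either:
- the recorded year is before the year of the reference date, or
- the years are equal and the recorded month is before that of the reference date.

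This matches the earlier-year branch in SAP 5.3.3.4 and leaves every other case as it is. The cost is one clause in the SAP and the matching condition in the program. A short note on whether axitinib cumulative dose runs to an imputed stop date would also settle the RDI question.

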#### **5.3.3. Imputation rules for date of last contact and efficacy assessments**

##### **5.3.3.1. Date of last contact**

The date of last contact will be derived for patients not known to have died at the analysis cut-off using the latest complete date among the following:

- All patient assessment dates (blood draws (laboratory, PK), vital signs, performance status, ECG, tumor assessments)
- Start and end dates of anti-cancer therapies administered after study treatment discontinuation.
- AE start and end dates
- Last date of contact collected on the 'Survival Follow-up' eCRF (do not use date of survival follow-up assessment unless status is 'alive')

- Study drug start and end dates
- Randomization date
- Withdrawal of consent date
- Date of discontinuation on disposition eCRF pages (do not use if reason for discontinuation is lost to follow-up).

Only dates associated with actual examinations of the patient will be used in the derivation. Dates associated with a technical operation unrelated to patient status such as the date a blood sample was processed will not be used. Assessment dates after the cut-off date will not be applied to derive the last contact date.

### **5.3.3.2. Death date**

Missing or partial death dates will be imputed based on the last contact date:

- If the date is missing it will be imputed as the day after the date of last contact
- If the day or both day and month is missing, death will be imputed to the maximum of the full (non-imputed) day after the date of last contact and the following:
  - Missing day: 1st day of the month and year of death
  - Missing day and month: January 1st of the year of death

### **5.3.3.3. Tumor assessments**

All investigation dates (eg, X-ray, CT scan) must be completed with day, month and year.

If there are multiple scan dates associated with an evaluation, ie, radiological assessments occur over a series of days rather than the same day, the choice of date of assessment could impact the date of progression and/or date of response. If there are multiple scan dates associated with an evaluation, the earliest of the scan dates associated with the evaluation will be used as the date of assessment.

If one or more investigation dates for an evaluation are incomplete but other investigation dates are available, the incomplete date(s) are not considered for calculation of the assessment date and assessment date is calculated as the earliest of all investigation dates (eg, X-ray, CT-scan).

If all measurement dates for an evaluation have no day recorded, the 1st of the month is used.

If the month is not completed, for any of the investigations for an evaluation, the respective assessment will be considered to be at the date which is exactly between the previous and the following assessment. If both a previous and following assessments are not available, this assessment will not be used for any calculations.

#### 5.3.3.4. Date of start of new anti-cancer therapy

Incomplete dates for start date of new anti-cancer therapy (drug therapy, radiation, surgery) will be imputed as follows and will be used for determining censoring dates for efficacy analyses and in the derivation of the end of on-treatment period. PD date below refers to PD date by investigator assessment.

- The end date of new anti-cancer therapy will be included in the imputations for start date of new anti-cancer therapy. If the end date of new anti-cancer therapy is
  - completely missing then it will be ignored in the imputations below
  - partially missing with only year (YYYY) available then the imputations below will consider 31DECYYYY as the end date of the new anti-cancer therapy
  - partially missing with only month and year available then the imputations below will consider the last day of the month for MMMYYYY as the end date of the new anti-cancer therapy
- For patients who have not discontinued study treatment at the analysis cut-off date, last dose of study treatment is set to the analysis cut-off date in the imputations below.
- If the start date of new anti-cancer therapy is completely or partially missing then the imputed start date of new anti-cancer therapy is derived as follows:
  - Start date of new anti-cancer therapy is completely missing  
Imputed start date = min [max(PD date + 1, last dose of study treatment + 1), end date of new anti-cancer therapy]
  - Only year (YYYY) for start of anti-cancer therapy is available  
IF YYYY < Year of min [max(PD date + 1, last dose of study treatment + 1), end date of new anti-cancer therapy] THEN imputed start date = 31DECYYYY;  
ELSE IF YYYY = Year of min [max(PD date + 1, last dose of study treatment + 1), end date of new anti-cancer therapy]  
THEN imputed start date = min [max(PD date + 1, last dose of study treatment + 1), end date of new anti-cancer therapy]  
ELSE IF YYYY > Year of min [max(PD date + 1, last dose of study treatment + 1), end date of new anti-cancer therapy]  
THEN imputed start date = 01JANYYYY
  - Both Year (YYYY) and Month (MMM) for start of anti-cancer therapy are available  
IF  
YYYY = Year of min [max(PD date + 1, last dose of study treatment + 1), end date of new anti-cancer therapy], AND  
MMM < Month of min [max(PD date + 1 day, last dose of study treatment + 1 day), end date of new anti-cancer therapy]

THEN

imputed start date = DAY (Last day of MMM) MMM YYYY ;

ELSE IF

YYYY = Year of min [max(PD date + 1, last dose of study treatment + 1), end date of new anti-cancer therapy], AND

MMM = Month of min [max(PD date + 1 day, last dose of study treatment + 1 day), end date of new anti-cancer therapy]

THEN

imputed start date = min [max(PD date + 1 day, last dose of study treatment + 1 day), end date of new anti-cancer therapy];

ELSE IF

YYYY = Year of min [max(PD date + 1, last dose of study treatment + 1), end date of new anti-cancer therapy], AND

MMM > Month of min [max(PD date + 1 day, last dose of study treatment + 1 day), end date of new anti-cancer therapy]

THEN

imputed start date = 01 MMM YYYY;

ELSE IF

YYYY < Year of min [max(PD date + 1, last dose of study treatment + 1), end date of new anti-cancer therapy]

THEN

imputed start date = DAY (Last day of MMM) MMM YYYY;

ELSE IF

YYYY > Year of min [max(PD date + 1, last dose of study treatment + 1), end date of new anti-cancer therapy]

THEN

imputed start date = 01 MMM YYYY.

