8.2. Reporting Period

For SAEs, the active reporting period to Pfizer or its designated representative begins from the time that the patient provides informed consent, which is obtained prior to the patient's participation in the study, ie, prior to undergoing any study-related procedure and/or receiving investigational product, through and including 90 calendar days after the last administration of the study treatment.

SAEs occurring to a patient after the active reporting period has ended should be reported to the sponsor if the investigator becomes aware of them; at a minimum, all SAEs that the investigator believes have at least a reasonable possibility of being related to investigational product are to be reported to the sponsor.

AEs (serious and non-serious) should be recorded on the CRF from the time the patient has taken at least one dose of study treatment through and including 90 calendar days after the last administration of study treatment. If a patient begins a new anticancer therapy, the AE reporting period for nonserious AEs ends at the time the new treatment is started. Death must be reported if it occurs during the SAE reporting period after the last dose of study treatment, irrespective of any intervening treatment.

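### Incomplete start dates for new anti-cancer drugs can end the on-treatment safety window on the day of the last dose

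*SAP*

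**What the plan says.** SAP 5.2.7 (and 3.5.1) runs the on-treatment period from first dose "through minimum (30 days + last dose of study treatment, start day of new anti-cancer drug therapy – 1 day". It adds: "Safety data collected outside the on-treatment period as described above will be listed and flagged in listings but not summarized".

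If the drug start date is incomplete, SAP 5.2.5 refers to the rule in 5.3.3.4, using only the follow-up cancer therapy pages. SAP 5.2.6 refers to the same rule for efficacy censoring, but also draws on radiation and surgery pages. 5.3.3.4 confirms that the imputed dates serve both purposes: they "will be used for determining censoring dates for efficacy analyses and in the derivation of the end of on-treatment period".

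The rule works from an anchor date:

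- Completely missing: "Imputed start date = min [max(PD date + 1, last dose of study treatment + 1), end date of new anti-cancer therapy". The bracketed quantity is the anchor.
- Year, or month and year, equal to the anchor's: the anchor itself.
- Known period after the anchor's: its first day ("THEN imputed start date = 01JANYYYY" for a year, "imputed start date = 01 MMM YYYY" for a month).
- Known period before the anchor's: its last day (for a month, "imputed start date = DAY (Last day of MMM) MMM YYYY").

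Protocol 8.2 governs what is collected: "If a patient begins a new anticancer therapy, the AE reporting period for nonserious AEs ends at the time the new treatment is started".

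**The concern.** For efficacy, placing an unknown start just after PD or the last dose is a sensible convention. For safety, the same date closes the window in which events count as treatment-emergent. If PD does not push the anchor later, the anchor is the first day after the last dose, so an unknown date is treated as an immediate switch of therapy.

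That setting is to be expected here. Protocol 5.3.3.3 allows dosing while PD is being confirmed, and in some cases beyond confirmed PD, so first documented PD will often precede the last dose.

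The imputed date can also contradict the record. Under Protocol 8.2, a nonserious event properly recorded on day 10 after the last dose shows that no new therapy had started by then. The rule still classes it as off-treatment. SAP 5.3.2.2 leans the other way for missing adverse-event onset dates, which it sets to the start of study treatment so that the event is counted.

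At stake are the summaries of treatment-emergent adverse events and SAEs, worst-grade laboratory results and notable ECG values, in a Phase 1b study whose primary objective is safety.

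**Working it through.** The plan gives no figure for this effect. Its one figure on capturing adverse events, at least 90% probability of seeing one or more in 40 patients at 6% incidence (SAP 5.1.1), reproduces as 1 − 0.94^40 = 91.6% and is not in dispute.

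**Inputs from the SAP.** With L the last dose date and S the drug start date, anchor A = min[max(PD + 1, L + 1), therapy end date]. Post-dose days kept = min(30, S − 1 − L), not below 0. The SAP does not say what the maximum returns without PD; L + 1 is assumed.

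**Single cases, L = 10 March, no therapy end date recorded**

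| PD | Recorded start | True start | Imputed start | Days kept | Days with true date |
|---|---|---|---|---|---|
| 5 March | missing | 15 April | 11 March | 0 | 30 |
| 5 March | March | 31 March | 11 March | 0 | 20 |
| 5 March | April | 25 April | 1 April | 21 | 30 |
| 30 March | missing | 15 April | 31 March | 20 | 30 |
| 14 April | missing | 15 May | 15 April | 30 | 30 |
| 15 May | March | 15 March | 31 March | 20 | 4 |

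The first three rows show the defect. The next two show a later PD protecting part or all of the window. The last shows the rule making the window too long.

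**Averages over a grid (assumed).** Last dose on each day of one year, true start 1 to 90 days later, no therapy end date. With true dates the mean is (0 + 1 + … + 29 + 60 × 30)/90 = 2235/90 = 24.8 days. The alternative is the latest start compatible with the recorded parts, with no shortening when all parts are missing.

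| PD relative to last dose | Recorded start | SAP rule | Alternative | True |
|---|---|---|---|---|
| none, or 5 days before | missing | 0.0 | 30.0 | 24.8 |
| none, or 5 days before | year only | 2.6 | 29.8 | 24.8 |
| none, or 5 days before | month and year | 19.9 | 28.2 | 24.8 |
| 14 days after | missing | 14.0 | 30.0 | 24.8 |
| 14 days after | month and year | 23.2 | 28.2 | 24.8 |
| 28 days after | missing | 28.0 | 30.0 | 24.8 |
| 45 days after | missing | 30.0 | 30.0 | 24.8 |

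For a completely missing date, the SAP window is too short in 99% of grid cases (89/90) with PD absent or before the last dose, 83% with PD at +14 days, 68% at +28 and 0% at +45. It is too long in 0%, 16%, 31% and 33%.

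**Other assumed gaps, month and year known, PD absent or on or before the last dose**

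- Gap 14 to 42 days: 11.8 of 24.7 days lost (48%); 18% of such patients lose the whole window.
- Gap 7 to 60 days: 7.9 of 24.4 days lost (32%); 19% lose the whole window.

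**The case against.** The strongest reply is that little may be lost in practice, and most of it stands as a limit on the point.

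- Events outside the window remain in flagged listings, including all SAEs (SAP 6.6.1, 6.6.3). Immune-related events are counted to 90 days regardless of new therapy (SAP Appendix 1), and the 30-day death summary ignores it (SAP 6.6.2). End-of-treatment laboratory and vital-sign results have their own descriptive summaries (SAP 6.6.5.1, 6.6.6).
- New therapy is recorded at end of treatment and at follow-up Days 30, 60 and 90, so a drug started within 30 days may usually have a full date. About 55 patients are planned, and the number affected could be zero.

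A reader might infer that safety and efficacy share a single date. They share a rule: SAP 5.2.5 uses drug therapy only, while 5.2.6 adds curative radiation and resection.

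A reader might also infer that the error always favours a cleaner safety profile. It does not: a PD after the last dose moves the anchor later, and a start month before the anchor's goes to its last day, which can lengthen the window.

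Finally, a reader might want to move the efficacy date earlier too. For a missing start with PD after the last dose, that would place new therapy before an observed PD and turn a PFS event into a censored observation (SAP Table 4). The SAP's use of PD + 1 avoids this.

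None of this removes the defect where PD is absent or not later than the last dose.

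**Conclusion.** The point holds in limited form. With PD absent or on or before the last dose, and no earlier therapy end date to bring the anchor forward, a drug start date that is missing, or known only to the year or month of last dose + 1, leaves 0 of up to 30 post-dose days in the summaries. A known later month costs fewer days or none. Under the assumed gaps, month-and-year dates lose about a third to a half of the window on average.

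These sizes apply per affected patient and rest on the assumed gaps and on reading the anchor without PD as last dose + 1. Complete dates are unaffected, and the documents give no count of incomplete ones, so the effect on any table is unknown. This is a cheap improvement, not a threat to the study's conclusions.

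**What to change.** Add a safety-only clause to SAP 5.2.5 and 5.3.3.4. For the end of the on-treatment period, impute an incomplete drug start as the latest date compatible with the record: the last day of a known month or 31 December of a known year, never after a recorded therapy end date. If the start is completely missing, do not end the window before last dose + 30 days unless a recorded end date requires it. Leave the efficacy rule unchanged.

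The cost is a few lines and one derived variable. The downside is that an event after the new drug began may occasionally count as on-treatment. Because nonserious events stop being collected at that point, this mainly concerns SAEs and laboratory or ECG results.

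In the setting at issue, the mean error on the grid changes from 24.8 days short to 5.2 long (missing), from 22.2 short to 5.0 long (year only), and from 4.9 short to 3.4 long (month and year). The gain is not universal: with PD 14 days after the last dose and month and year known, it changes from 1.6 short to 3.4 long. With PD at 28 days and a missing date, it changes from 3.2 to 5.2 long. The case for the change there is only that it errs towards keeping events.
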